11.0 Data Quality Assurance

Computer logic and manual checks will be created to identify items such as inconsistent study dates. Any necessary corrections will be made to the eCRF.

12.0 Use of Information

All information concerning upadacitinib and AbbVie operations, such as AbbVie patent applications, formulas, manufacturing processes, basic scientific data, or formulation information, supplied by AbbVie and not previously published is considered confidential information.

The information developed during the conduct of this clinical study is also considered confidential and will be used by AbbVie in connection with the development of upadacitinib. This information may be disclosed as deemed necessary by AbbVie to other clinical investigators, other pharmaceutical companies, and to governmental agencies. To allow for the use of the information derived from this clinical study and to ensure complete and thorough analysis, the investigator is obligated to provide AbbVie with complete test results and all data developed in this study and to provide direct access to

source data/documents for study-related monitoring, audits, IEC/IRB review, and regulatory inspection.

This confidential information shall remain the sole property of AbbVie, shall not be disclosed to others without the written consent of AbbVie, and shall not be used except in the performance of this study.

The investigator will maintain a confidential subject identification code list of all subjects enrolled in the study, including each subject's name, subject number, address, phone number and emergency contact information. This list will be maintained at the study site with other study records under adequate security and restricted access and will not be retrieved by AbbVie.

Any exploratory research/validation studies that may be done using the samples from this study will be experimental in nature and the results will not be suitable for clinical decision making or patient management, hence, neither the investigator, the subject, nor the subject's physician (if different from the investigator) will be informed of individual subject results, should analyses be performed, nor will anyone not directly involved in this research. Correspondingly, researchers will have no access to subject identifiers. Individual results will not be reported to anyone not directly involved in this research other than for regulatory purposes. Aggregate data from exploratory research/validation studies from this study may be used in scientific publications or presented at medical conventions. Exploratory research/validation data will be published or presented only in a way that does not identify any individual subject.

13.0 Completion of the Study

The investigator will conduct the study in compliance with the protocol and complete the study within the timeframe specified in the contract between the investigator (Director of the Site in Japan) and AbbVie. Continuation of this study beyond this date must be mutually agreed upon in writing by both the investigator (Director of the Site in Japan) and AbbVie. The investigator will provide a final report to the IEC/IRB following

conclusion of the study and will forward a copy of this report to AbbVie or their representative.

The investigator (Director of the Site in Japan) must submit, maintain, and archive any records related to the study according to ICH GCP and all other applicable regulatory requirements. If the investigator (Director of the Site in Japan) is not able to retain the records, he/she must notify AbbVie to arrange alternative archiving options.

AbbVie will select the signatory investigator from the investigators who participate in the study. Selection criteria for this investigator will include level of participation as well as significant knowledge of the clinical research, investigational drug and study protocol. The signatory investigator for the study will review and sign the final study report in accordance with the European Agency for the Evaluation of Medicinal Products (EMA) Guidance on Investigator's Signature for Study Reports.

The end-of-study is defined as the date of the last subject's last visit.

Appendix A. Responsibilities of the Clinical Investigator

Clinical research studies sponsored by AbbVie are subject to the Good Clinical Practices (GCP) and local regulations and guidelines governing the study at the site location. In signing the Investigator Agreement in Section 14.0 of this protocol, the investigator is agreeing to the following:

1. Conducting the study in accordance with the relevant, current protocol, making changes in a protocol only after notifying AbbVie, except when necessary to protect the safety, rights or welfare of subjects.
2. Personally conducting or supervising the described investigation(s).
3. Informing all subjects, or persons used as controls, that the drugs are being used for investigational purposes and complying with the requirements relating to informed consent and ethics committees (e.g., independent ethics committee [IEC] or institutional review board [IRB]) review and approval of the protocol and amendments.
4. Reporting adverse experiences that occur in the course of the investigation(s) to AbbVie and the site director.
5. Reading the information in the Investigator's Brochure/safety material provided, including the instructions for use and the potential risks and side effects of the investigational product(s).
6. Informing all associates, colleagues, and employees assisting in the conduct of the study about their obligations in meeting the above commitments.
7. Maintaining adequate and accurate records of the conduct of the study, making those records available for inspection by representatives of AbbVie and/or the appropriate regulatory agency, and retaining all study-related documents until notification from AbbVie.
8. Maintaining records demonstrating that an ethics committee reviewed and approved the initial clinical investigation and all amendments.

9. Reporting promptly, all changes in the research activity and all unanticipated problems involving risks to human subjects or others, to the appropriate individuals (e.g., coordinating investigator, institution director) and/or directly to the ethics committees and AbbVie.
10. Following the protocol and not make any changes in the research without ethics committee approval, except where necessary to eliminate apparent immediate hazards to human subjects.

Appendix B. List of Protocol Signatories

Name	Title	Functional Area
		Clinical
		Clinical
		Pharmacovigilance
		Statistics
		Statistics
		Clinical Operations
		Bioanalysis
		Clinical Pharmacology and Pharmacometrics

Appendix C. Study Activities (Part 1; 8 Week Double-Blind Induction and Part 2; Extended Treatment Period)

Activity	Part 1 – 8-Week Double-Blind Induction								Part 2 – Extended Treatment Period				Un-scheduled Visit ^d	30-Day FU ^e
	Screening ^a	Baseline (Week 0) ^b	Week 2	Week 4	Week 6	Week 8 ^c	Week 10	Week 12	Week 14	Week 16	PD Visit			
Informed Consent	X													
Inclusion/Exclusion	X	X ^f												
Medical/Surgical History	X	X ^f												
Prior and Concomitant Medications [#]	X	X ^f	X	X	X	X	X	X	X	X	X	X	X	
Physical Exam ^{g,+}	X ^g	X	X	X	X	X	X	X	X	X	X	X	X	
Tanner Stage ^g	X (16 – 17 years old subjects only)													
Vital Signs ^{h,+}	X ^h	X	X	X	X	X ^h	X	X	X	X ^h	X	X	X	
Schedule Endoscopy [#]	X		X	X				X						
Endoscopy ⁱ /Biopsy ^{h,+}	X					X				X				
12-Lead ECG ^{k,+}	X					X				X		X	X	
Chest X-ray ^{l,+}	X													

Activity	Part 1 – 8-Week Double-Blind Induction										Part 2 – Extended Treatment Period				Un-scheduled Visit ^d	30-Day FU ^e				
	Screening ^a	Baseline (Week 0) ^b	Week 2	Week 4	Week 6	Week 8 ^c	Week 10	Week 12	Week 14	Week 16	PD Visit	Week 10	Week 12	Week 14			Week 16			
PPD Skin Test or QuantiFERON-TB Gold Plus Test ^{m,+}	X																			
Latent TB Risk Assessment Form [#]	X																			X
Chemistry and Hematology ^{n,+}	X	X	X	X	X	X	X	X	X	X	X	X	X	X	X	X	X	X	X	X
Lipid Test ^{n,+}		X									X									
Optional biologic drug level ^o	X																			
Urinalysis ^{p,+}	X	X	X	X	X	X	X	X	X	X	X	X	X	X	X	X	X	X	X	X
Pregnancy Test ^{q,+}	X	X	X	X	X	X	X	X	X	X	X	X	X	X	X	X	X	X	X	X
Review and document pregnancy avoidance recommendations in the source records with females of childbearing potential [#]	X	X	X	X	X	X	X	X	X	X	X	X	X	X	X	X	X	X	X	X

Activity	Part 1 – 8-Week Double-Blind Induction								Part 2 – Extended Treatment Period				Un-scheduled Visit ^d	30-Day FU ^e
	Screening ^a	Baseline (Week 0) ^b	Week 2	Week 4	Week 6	Week 8 ^c	Week 10	Week 12	Week 14	Week 16	PD Visit			
HBV and HCV Screening ^{†,††}	X					X ^s								
HIV Ab	X													
Beta-D-Glucan (Japan Only)	X													
hs-CRP [¶]	X	X	X	X	X	X	X	X	X	X	X	X	X	
Stool Sample (C. difficile toxin)	X													
Provide Stool Kit [#]	X	X			X	X ^t			X					
Stool Sample (Fecal calprotectin) ^{†††}		X	X			X	X	X			X	X	X	
Reminder: Stool Sample for exploratory research and validation studies (Optional – See Appendix D) ^{†††}		X	X			X	X	X			X	X	X	
Upadacitinib (ABT-494) Concentration (PK Assay) ^{¶¶}			X ^u		X ^u	X ^u							X ^u	

Activity	Part 1 – 8-Week Double-Blind Induction								Part 2 – Extended Treatment Period				Un-scheduled Visit ^d	30-Day FU ^e
	Screening ^a	Baseline (Week 0) ^b	Week 2	Week 4	Week 6	Week 8 ^c	Week 10	Week 12	Week 14	Week 16	PD Visit			
	Lymphocyte Subset ^{v,+}		X				X				X	X		
Samples for exploratory research and validation studies (Optional – See Appendix D) ^{t,-}		X	X			X				X	X			
Mayo Score [#]		X				X				X				
Partial Mayo Score/Adapted Partial Mayo [#]		X	X	X	X	X	X	X	X	X	X	X		
Patient Questionnaires: IBDQ, SF-36, EQ-5D-5L, WPAL, FACIT-F, PGIS, UC-SQ ^{v,#}		X				X				X				
PGIC ^{w,#}						X				X				
Monitor Adverse Events ^{x,#}		X	X	X	X	X	X	X	X	X	X	X	X	X

Activity	Part 1 – 8-Week Double-Blind Induction						Part 2 – Extended Treatment Period				Un-scheduled Visit ^d	PD Visit	30-Day FU ^e	
	Screening ^a	Baseline (Week 0) ^b	Week 2	Week 4	Week 6	Week 8 ^c	Week 10	Week 12	Week 14	Week 16				
		X	X	X	X	X	X	X	X	X				X
Dispense Daily Diary ^y	X													
Daily Diary Review ^{y,z}		X	X	X	X	X	X	X	X	X	X	X		
Study Drug Dispensing/ Administration ^{z,aa,#}		X	X	X	X	X ^{bb}	X	X						

PD = premature discontinuation

- # Study activity that can be performed by phone/virtually when an onsite study visit is not possible due to COVID-19, if allowed by local regulations. This is applicable for the following visits: Week 2, 4, 6, 8, 10, 12, 14, 16, PD and 30 day Follow up. All screening and Baseline visit procedures must be completed at the study site.
- + Study activity that can be performed at a local centre when an onsite study visit is not possible due to COVID-19, if allowed by local regulations. This is applicable for the following visits: Week 2, 4, 6, 8, 10, 12, 14, 16, PD and 30 day Follow up. All screening and Baseline visit procedures must be completed at the study site.
- = Study activity that cannot be performed by phone/virtually or at a local centre when an onsite study visit is not possible due to COVID-19. All screening and Baseline visit procedures must be completed at the study site.
- a. The Screening period will be a maximum of 35 days. The Baseline Visit can be scheduled and a subject randomized at any point during this period once all eligibility criteria have been met.
- b. The Baseline Visit date will serve as the reference for all subsequent visits. A \pm 3-day window is permitted around all study visits. Where COVID-19 affects an onsite scheduled Visit a \pm 7-day window is permitted for all visits after the Baseline visit.
- c. At Week 8 of Part 1, if a subject is a clinical non-responder, Week 8 will be used as the Baseline Visit for Part 2 (Extended Treatment Period).
- d. Visits for dispensing new study drug in case of temperature excursion, loss or damage or visits to retest a lab are not considered an Un-scheduled Visit. Un-scheduled visits according to this table are for purposes when the subject is coming in for a visit for evaluation and assessment.

- e. Subjects will be contacted 30 days following study drug discontinuation for an assessment of any new or ongoing AEs, except those subjects who will continue on to Substudy 3 of Study M14-234, this will not be required until the subject completes the UC program. The home pregnancy test results will be reported at this visit, as applicable, and if a pregnancy is identified, the pregnancy must be reported to AbbVie as outlined in Section 6.1.6. The 30 day follow up visit should not take place sooner than 30 days after the last dose of study drug, the allowable visit window is dependent upon what phase of the study the subject was at when discontinuing study drug. During Part 1 and 2 of the induction period a + 3 day window (30 to 33 days after last study drug date) is allowed.
- f. Update inclusion/exclusion, medical/surgical history information, and prior and concomitant therapy to assure subject eligibility.
- g. In Part 1, Physical examinations performed at Screening, Baseline, Week 8/PD and Part 2 at Week 16/PD Visits are full physical examinations which must include an assessment of extra-intestinal manifestations (EIMs). Physical exams at all other visits are symptom-based as necessary. Assessment of EIMs are required at every visit. For subjects 16 or 17 years of age a Tanner Stage check is to be completed during the physical examination at the screening visit, this may be completed by the investigator or by self-assessment (completed by the subject/legally authorized representative) per local requirements.
- h. Height (with shoes off) will be measured at Screening only for subjects \geq 18 years of age. For Subjects 16 or 17 years of age, where locally permitted, height (with shoes off) will be measured at screening, Week 8 and Week 16.
- i. Subjects will undergo a full colonoscopy with biopsy for histologic assessment during Screening, and a full colonoscopy or flexible sigmoidoscopy, depending on the extent of disease at Screening, at Week 8. For subjects in Part 2 (Extended Treatment Period), an endoscopy will be performed at Week 16, for this a flexible sigmoidoscopy is recommended, however the use of flexible rectosigmoidoscopy or colonoscopy will be based on the investigator's discretion per local practice.
- j. Appropriate documentation of biopsy results consistent with the diagnosis of UC, in the assessment of the investigator, must be available in order to confirm the subject's eligibility for the study. If this documentation is not available a diagnostic biopsy from the most affected observed area of the colon must be performed during the Screening endoscopy and evaluated by a qualified local pathologist and the results reviewed by the investigator. Biopsies to rule out current dysplasia and colon cancer may be taken during any study endoscopy per the investigator's discretion and evaluated by the local pathologist. During all endoscopies, up to 3 sets of biopsies will be taken (see Section 5.3.1.1 for details about biopsy sampling).
- k. Subjects with normal ECG within 90 days of Screening will not require a repeat ECG, if documentation is available. The Week 8 ECG will serve as the Baseline ECG for Part 2 (Extended Treatment Period), as applicable or for Baseline of Study M14-234 Substudy 3. For subjects who enter Part 2 (Extended Treatment Period), Week 16 ECG will serve as the baseline ECG for Study M14-234 Substudy 3.
- l. Chest x-ray includes posterior-anterior [PA] and lateral views. Subjects with normal chest x-ray within 3 months of Screening will not require a repeat chest x-ray, if documentation is available. In Japan, a CT scan of the chest may be performed in lieu of a CXR, at investigator's discretion.
- m. If a subject had a negative QuantiferON-TB Gold Plus test within 90 days of Screening and source documentation is available, the test does not need to be repeated, provided nothing has changed in the subject's medical history to warrant a repeat test. PPD skin test is only to be used if the site is unable to perform the QuantiferON-TB Gold Plus testing and is to be read 48 to 72 hours after placement.
- n. It is requested to have a minimum of 8 hours fasting before any chemistry and lipid. If a subject is not able to fast when necessary, due to unforeseen circumstances, the non-fasting status will be recorded in study source documentation test.

- p. During screening, biologic drug levels may be optionally assessed at the investigator's discretion as an alternative to completing the required washout period: (1) infliximab and natalizumab: may be tested approximately 4 weeks or later from the last dose; (2) adalimumab, certolizumab, golimumab, or vedolizumab: may be tested approximately 6 weeks or later from the last dose; (3) ustekinumab: may be tested approximately 8 weeks or later from the last dose.
- p. The Central Laboratory will perform the urinalysis macro and micro (if applicable). A microscopic analysis will be performed by the central laboratory, in the event the dipstick results show leukocytes, nitrite, ketone, protein, blood, or glucose value of greater than a trace. Sites will not be provided with urinalysis dipsticks.
- q. A serum pregnancy test will be performed on all women of childbearing potential at Screening. In Part 1, a urine pregnancy test will be performed at the site at Baseline and at Weeks 2, 4, 6, 8 and PD Visits. In Part 2 (Extended Treatment Period), a urine pregnancy test will be done at Weeks 10, 12, 14 and 16, and a home pregnancy test will be performed at the 30-Day Follow-up Visit, if applicable, for all women of child bearing potential. If any urine pregnancy test is positive, a serum pregnancy test will be performed by the central laboratory. If a pregnancy is identified, the pregnancy must be reported to AbbVie as outlined in Section 6.1.6.
- r. Subjects will be tested for the presence of the hepatitis B and C virus (HBV and HCV) at Screening. A positive result for the hepatitis B surface antigen (HBs Ag) or hepatitis C (HCV RNA detectable for any subject with positive anti-HCV AB) will be exclusionary. For subjects who are negative for HBsAg but positive for core antibody (HBcAb), HBV DNA PCR will be performed and any result that meets or exceeds detection sensitivity will be exclusionary. HBV testing is done every 12 weeks where required.
- s. For Japan subjects only: Subjects with positive HBs Ab and/or positive HBc Ab results at Screening should have HBV-DNA PCR test performed at Week 8 in the induction period; in cases where recurrence of HBV-DNA is observed, the subject should be discontinued from the study. This measure is not necessary in patients with history of HBV vaccination and positive HBs Ab result.
- t. Stool sample will be collected at each time point indicated. For the visit that an endoscopy will be conducted, stool sample should be collected prior to the endoscopy. If a sample cannot be obtained during the site visit, the site will give instructions and a stool sample supply kit (supplies will be provided at the time-points indicated). All stool samples should be collected before any bowel preparation for endoscopy is started and should be returned to the site within 3 days of collection. Stool sample supply kit to be provided at Week 8 visit for subjects entering into the extended treatment program.
- u. Reference Section 5.3.2.1 regarding PK sample collection. The PK sample at Week 8 will be the baseline PK sample for Study M14-234 Substudy 3. PK should only be collected at the Premature discontinuation visit if the subject discontinues before the Week 8 visit, it is not relevant for subjects discontinuing during Part 2.
- v. Blood samples will be collected at the visits indicated and will be utilized to assess effects of upadacitinib inhibition on certain lymphocyte subsets, including T (CD4+ and CD8+) cells, B (CD19+) cells, natural killer (NK) cells, and natural killer-T (NKT) cells.
- w. IBDQ = Inflammatory Bowel Disease Questionnaire; SF-36 = Short-Form 36; EQ-5D-5L = European Quality of Life 5 Dimensions 5 Levels; WPAI = Work Productivity and Activity Impairment; FACIT F = Functional Assessment of Chronic Illness Therapy – Fatigue; PGIC = Patient Global Impression of Change; UC-SQ = UC Symptoms Questionnaire. PGIS = Patient Global Impression of Severity (only at select sites).
- x. Collection of Serious Adverse Events (SAEs) begins the day the subject signs the informed consent. During each study visit subjects will also be asked to report UC related Health Care Resource Utilization (Unscheduled Outpatient Visits, Emergency Room Visits and Hospitalizations and surgeries) and will be captured as a part of supplemental Health Care Resource Utilization (HCRU) form of AE collection in EDC.

- y. Subjects will be dispensed the subject diary at Screening and will be trained on how to complete the diary by site staff during the Screening Visit. All subjects should complete their subject diary on a daily basis throughout the entire study, including during hospitalizations whenever possible. The diary will be reviewed by site personnel with the subject at each visit and collected at the Final/PD Visit.
- z. Study drug will be dispensed for once daily oral intake and should be taken at the same time each day.
- aa. When central or local labs cannot be collected as scheduled in the protocol during the period of COVID-19 pandemic, drug may be dispensed if the following criteria are confirmed. (1) There is at least 1 post-Baseline lab assessment (either Week 2 or Week 4 visit) AND (2) The investigator feels it is safe to continue based on prior labs and a phone/video call AND (3) No longer than 4 weeks have passed from the last safety lab tests.
- bb. If a subject is entering Part 2 (Extended Treatment Period), investigational product will be dispensed at this visit. This is not applicable for subjects in Part 1 who are responders and move into Study M14-234 Substudy 3 at Week 8.

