HBV serologic test results will be interpreted and managed as shown in [Figure 2](#).

- A positive result for HBs Ag will be exclusionary.
- A negative result for HBs Ag will trigger automatic reflex testing for core antibodies (HBc Ab) and surface antibodies (HBs Ab).
- For a subject who has had an HBV vaccination (should document in the medical history), a positive test result for HBs Ab is expected, the HBV DNA PCR qualitative testing is **not** required and the subject may be enrolled (Scenario B).
- A negative test result for HBc Ab does **not** require HBV DNA PCR qualitative testing and the subject may be enrolled (Scenarios A and B).
- A positive test result for HBc Ab requires HBV DNA PCR testing (automatic reflex testing) (Scenarios C and D).
- A positive result for HBV DNA or a result that exceeds detection sensitivity will be exclusionary.
- A subject with a negative result for HBV DNA may be enrolled.

Figure 2. Interpretation and Management of HBV Serologic Test Results

* A positive test result for HBs Ab is expected for subjects who have had a HBV vaccination. For subjects without a history of HBV vaccination (and for subjects in Japan) a positive result for HBs Ab/anti-HBs requires HBV DNA PCR testing.

** Where mandated by local requirements; subjects with HBs Ab+ and/or HBc Ab+ and negative HBV DNA at Screening should have HBV DNA PCR testing performed approximately every 12 weeks. HBV DNA PCR testing every 12 weeks is not necessary when the subject has a history of HBV vaccine and HBs Ab+ and HBc Ab-. If necessary, HBV DNA PCR may be tested at unscheduled visits.

COVID-19 Pandemic-Related Acceptable Protocol Modifications

In the event that the HBV DNA PCR cannot be performed for subjects who require the test due to study modifications related to the COVID-19 pandemic, perform the HBV DNA PCR at the next earliest feasible visit or arrange to have it completed by a local laboratory.

Hepatitis C

Blood samples for Hepatitis C serology will be obtained at the Screening Visit. A positive HCV Ab will trigger an HCV RNA test. A subject will not be eligible for study participation if test results indicate active Hepatitis C (HCV RNA detectable in any subject with anti HCV Ab).

HIV

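### Minor, wrong as written: Appendix C footnote s waives the Japan-only Week 8 HBV DNA PCR without requiring a negative HBc Ab

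*Protocol*

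**What the plan says.** Protocol Appendix C, footnote s, applies to Japan only. Its scope is: "Subjects with positive HBs Ab and/or positive HBc Ab results at Screening should have HBV-DNA PCR test performed at Week 8". The consequence of a positive result is that "in cases where recurrence of HBV-DNA is observed, the subject should be discontinued from the study". The last sentence is the waiver: "This measure is not necessary in patients with history of HBV vaccination and positive HBs Ab result".

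The other HBV rules are in Section 5.3.1.1 (Hepatitis B) and Section 6.1.7:

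- Screening reflex: "A positive test result for HBc Ab requires HBV DNA PCR testing (automatic reflex testing) (Scenarios C and D"). No vaccination exception is attached.
- Figure 2, note *: it names subjects with no vaccination history, "(and for subjects in Japan) a positive result for HBs Ab/anti-HBs requires HBV DNA PCR testing".
- Figure 2, note **: where local rules mandate it, subjects positive for either antibody with negative HBV DNA at Screening "should have HBV DNA PCR testing performed approximately every 12 weeks". This repeat testing "is not necessary when the subject has a history of HBV vaccine and HBs Ab+ and HBc Ab" negative (the note prints a minus sign after the last word quoted).
- Table 4 (AST or ALT): HBc Ab-positive subjects with a negative Screening PCR, whatever their HBs Ab result, get a PCR within 1 week if ALT exceeds 5 × ULN, or if ALT or AST exceeds 3 × ULN without a readily identified cause.

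**The concern.** The two waivers cover the same serology group and differ by one condition. Note ** releases a vaccinated, HBs Ab-positive subject only if HBc Ab is negative. Footnote s releases that subject whatever the HBc Ab result.

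Vaccination explains a positive HBs Ab, and Section 5.3.1.1 says that result is expected after vaccination. The protocol gives vaccination no such role for a positive HBc Ab. HBc Ab is the marker it uses to trigger PCR at Screening and after an ALT/AST rise.

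Week 8 is the only post-screening HBV test marked in the Appendix C grid, and a positive result there leads to discontinuation. A subject who skips it may go on to 8 more weeks of 45 mg in Part 2, or to the 52-week maintenance study. The stake is the safety monitoring of individual subjects, not the trial's inference.

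**Working it through.** No power or error-rate calculation applies. The check applies each rule to one subject: in Japan, HBs Ag negative, vaccinated, HBs Ab positive, HBc Ab positive, Screening HBV DNA negative.

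| Rule | Result for this subject |
|---|---|
| Section 5.3.1.1, Screening reflex for HBc Ab | PCR required |
| Section 5.3.1.1, Figure 2 note * (Japan) | Screening PCR required |
| Section 5.3.1.1, Figure 2 note ** | Not exempt; 12-weekly PCR if locally mandated |
| Section 6.1.7, Table 4 | PCR after a qualifying ALT/AST rise |
| Appendix C footnote s, first sentence | In scope at Week 8 |
| Appendix C footnote s, last sentence | Exempt at Week 8 |

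Only the last row lets vaccination excuse an HBc Ab-positive subject. If HBc Ab is negative instead, footnote s and note ** agree that repeat PCR is not needed. The disagreement is therefore confined to this one pattern.

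**Could the 12-weekly test replace the Week 8 test?** Inputs: a 12-week (84-day) interval from note ** and a screening period of at most 35 days (Section 5.1). Counted from the Screening test, the repeat falls due on study day 84 minus the days from that test to Baseline:

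- test 0 days before Baseline: 84 − 0 = day 84 (Week 12)
- test 28 days before: 84 − 28 = day 56 (Week 8)
- test 35 days before: 84 − 35 = day 49 (Week 7)

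So it falls due by Week 8 only if the Screening test was at least 28 days before Baseline. It falls earlier if a re-screened subject's older result is reused, which Section 5.1 allows up to 90 days. The documents do not say whether Japan mandates this testing.

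**Can rewording this version still change a Week 8 test?** Inputs: last randomization on 26 May 2020 (SAP Appendix D); a 7-day COVID-19 visit window (Appendix C, footnote b); protocol version dated 31 July 2020 (Synopsis).

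- Last Week 8 visit due: 26 May + 56 days = 21 July 2020; + 7 days = 28 July 2020.
- Gap to this version: 31 July − 28 July = 3 days.
- Last Week 16 visit due: 26 May + 112 days = 15 September 2020; + 7 days = 22 September 2020.
- Earliest randomization with Week 16 due on or after the version date: 31 July − 112 days = 10 April 2020.

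On-time Part 1 Week 8 tests were therefore complete before this version. Only Part 2 subjects randomized from 10 April to 26 May 2020 had a Week 16 visit due on or after its date. Appendix I reproduces the superseded footnote with the same waiver wording, so the earlier Week 8 visits were not covered by a stricter text.

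**The case against.** The best defence is that footnote s is shorthand. The Screening list in Section 5.3.1.1 also says that a vaccinated subject with positive HBs Ab needs no PCR, without stating that HBc Ab is negative. That bullet is tagged Scenario B, and the next one ties Scenarios A and B to a negative HBc Ab. Footnote s uses the same two-part condition, and its natural purpose is to release people whose only positive result is the one vaccination produces. This is probably what was meant. It does not settle the matter, because footnote s carries no scenario label, cross-reference or neighbouring rule that supplies the missing condition, and a site will follow what is printed.

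A reader might also infer that Japan falls below a standard the protocol keeps everywhere else. The documents do not support that. After Screening, routine repeat PCR applies only where mandated locally (note **; Appendix C footnote r). In a country without such a mandate, an HBc Ab-positive subject has a negative Screening PCR and the Table 4 trigger, which is what the exempted subject in Japan keeps. Chemistry is scheduled at every on-treatment visit, two weeks apart, so that trigger is checked repeatedly. The loss is of an additional Japan-only check.

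The objection that rewording comes too late for on-time Week 8 tests also stands. It is why a records query belongs in the fix.

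**Conclusion.** The point holds as a minor error in a stated rule. Followed literally, footnote s cancels its own test for a vaccinated subject positive for both antibodies, and no other HBV rule in the protocol lets vaccination do that for a positive HBc Ab.

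Per affected subject, the loss is the single post-screening HBV DNA test marked in the schedule. The partial safeguards are the negative Screening PCR, the Table 4 trigger, discretionary unscheduled PCR and any mandated 12-weekly PCR. The number affected is unknown and may be zero. Endpoints, alpha, power and analyses are untouched.

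A reader might infer that the sponsor meant to exempt these subjects, or that some went unmonitored. The documents show neither: the first is less likely than loose drafting, and no serology counts are given.

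The conclusion rests on the printed notes to Figure 2, since the figure itself is not shown. The timing rests on visits kept to schedule. Section 5.3.1.1 lets a PCR missed because of the pandemic be done at the next feasible visit, so a postponed Week 8 test could still come under this version.

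**What to change.** Amend the last sentence of footnote s so that the waiver needs three conditions: history of HBV vaccination, positive HBs Ab and negative HBc Ab. This matches note ** and leaves vaccinated, core-negative subjects exempt, so it adds no unnecessary testing.

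Also query the Japan Screening records for vaccinated subjects positive for both antibodies who have no post-screening HBV DNA result. For any still on treatment in this study, use the provision already in note **: "If necessary, HBV DNA PCR may be tested at unscheduled visits". On schedule, Part 2 treatment ended by 22 September 2020. For subjects who have moved on, pass the information to the follow-on study; its HBV rules are not in these documents, so no test should be prescribed from here.

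The cost is one footnote sentence, one query of serology already collected, and at most one assay per subject found.
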